## 12.2 Secondary Endpoints

### Eczema Area and Severity Index (EASI)

EASI score (as a secondary endpoint) will be assessed as:

- Percent change from baseline in EASI Total Score at each study visit
- Change from baseline in EASI Total Score at Weeks 1 and 2
- Proportion of subjects with a 75% or greater improvement in Eczema Area and Severity Index (EASI75) score from baseline to each study visit
- Proportion of subjects with a 50% or greater improvement in Eczema Area and Severity Index (EASI50) score from baseline to each study visit
- Proportion of subjects with a 90% or greater improvement in Eczema Area and Severity Index (EASI90) score from baseline to each study visit
- Proportion of subjects with a 100% or greater improvement in Eczema Area and Severity Index (EASI100) score from baseline to each study visit

### Body Surface Area (BSA)

The BSA affected by atopic dermatitis will be determined by the subject's hand method, where the subject's hand (including fingers) surface area is assumed to equal 1% of BSA.

BSA will be assessed as:

- Change from baseline in BSA involvement at each study visit

 INNOVADERM RESEARCH INC.	STATISTICAL ANALYSIS PLAN, Final V1.0Final 1.0
Protocol Number: AQR-151-212	Sponsor: Arcutis, Inc.

### **Worst Itch Numerical Rating Scale (WI-NRS)**

The WI-NRS has been developed as a simple, single item to assess the patient-reported severity of this symptom at its highest intensity during the previous 24-hour period. The WI-NRS will be determined by asking the subject's assessment of worst itch over the past 24 hours. The scale is from '0 to 10' ("no itch" to "worst imaginable itch"). Subjects will complete the WI-NRS pruritus assessment.

0	1	2	3	4	5	6	7	8	9	10
---	---	---	---	---	---	---	---	---	---	----

No itch

Worst  
imaginable itch

WI-NRS will be assessed as:

- Change from baseline in WI-NRS pruritus score at each study visit
- $\geq 4$ -point improvement from Baseline in WI-NRS pruritus score at each study visit for subjects with a Baseline WI-NRS  $\geq 4$
- $\geq 4$ -point improvement from Baseline in WI-NRS pruritus score at each study visit for subjects with a Baseline WI-NRS  $\geq 6$

### **Secondary Endpoint Analysis**

Descriptive statistics will be presented on all secondary endpoints by visit and treatment group.

A similar analysis approach as outlined for the primary endpoint will be used for all secondary continuous efficacy endpoints. The comparisons of each dose of ARQ-151 with the vehicle will be presented.

For categorical efficacy endpoints involving proportions (e.g. achievement of a 75% or greater improvement in EASI score from baseline at each study visit), a Cochran Mantel Haenszel test (CMH) controlling for the stratification variable will be performed. The comparisons of each dose of ARQ-151 with the vehicle will be presented.

Subgroup analyses by vIGA-AD strata and age-group will be performed on all secondary endpoints.

### **12.3 Exploratory Endpoints**

#### **Validated Investigator Global Assessment scale for Atopic Dermatitis (vIGA-AD)**

 INNOVADERM RESEARCH INC.	STATISTICAL ANALYSIS PLAN, Final V1.0Final 1.0
Protocol Number: AQR-151-212	Sponsor: Arcutis, Inc.

The vIGA-AD is a static evaluation of qualitative overall atopic dermatitis severity. This global assessment scale is an ordinal scale with five severity grades (reported only in integers of 0 to 4). Each grade is defined by a distinct and clinically relevant morphologic description that minimizes inter-observer variability (see [Appendix 4](#)). vIGA-AD is evaluated for the entire body except the scalp, palms, and soles.

vIGA-AD will be assessed as:

- Proportion of subjects with vIGA-AD score of ‘clear’ or ‘almost clear’ at each study visit
- Proportion of subjects with vIGA-AD score of ‘clear’ or ‘almost clear’ with a 2-point improvement from baseline at each study visit
- Change from baseline in vIGA-AD score at each study visit

### Exploratory Endpoint Analysis

Descriptive statistics will be presented on vIGA-AD by visit and treatment group.

A similar analysis approach as outlined for the primary endpoint will be used for the change from baseline in vIGA-AD. The comparisons of each dose of ARQ-151 with the vehicle will be presented.

For categorical efficacy endpoints involving proportions (e.g. proportion of subjects with vIGA-AD score of “clear” or “almost clear” at each study visit), a Cochran Mantel Haenszel test (CMH) controlling for the stratification variable will be performed. The comparisons of each dose of ARQ-151 with the vehicle will be presented.

## 13 SAFETY ANALYSIS

---

All safety analyses will be conducted using the safety population. Safety analyses will be presented for all subjects combined, and for adults and adolescents separately. No formal inferential statistics will be performed on safety assessments.

### 13.1 Adverse Events

Adverse events (AEs) will be coded according to the Medical Dictionary for Regulatory Activities (MedDRA), Version 22.0.

A treatment emergent adverse event (TEAE) is defined as an AE that started post application of study medication at the baseline visit or was present at treatment initiation but worsened during treatment, through study completion. See [Appendix 2](#) for handling of completely or partially missing dates for AEs. In the case where it is not possible to define an AE as treatment emergent or not, the AE will be classified as treatment emergent.

 INNOVADERM RESEARCH INC.	STATISTICAL ANALYSIS PLAN, Final V1.0Final 1.0
Protocol Number: AQR-151-212	Sponsor: Arcutis, Inc.

An overall summary table of adverse events will be provided. The number of events and the number and percentage of subjects who experienced AE, TEAE, TEAE by greatest reported relationship, TEAE by highest reported severity, related TEAE by highest reported severity, serious AE (SAE), serious TEAE, TEAE leading to study drug discontinuation, TEAE leading to study discontinuation, and AE leading to death will be presented.

Unless otherwise specified, a subject experiencing the same TEAE multiple times will be counted only once for the corresponding PT. Similarly, if a subject experiences multiple TEAEs within the same SOC, the subject will be counted only once for that SOC. TEAEs will be sorted by decreasing order of SOC and within each SOC the PT will be presented by decreasing order.

Frequency and percentage of subjects who experience TEAE will be summarized by SOC and PT within SOC.

Frequency and percentage of subjects who experience TEAE will be summarized by SOC, PT, and relationship. A treatment-related TEAE is defined as any TEAE that is assessed by the investigator as likely, probably, or possibly related to study treatment. TEAE that is assessed as unrelated or unlikely will be defined as not treatment-related. If a subject experiences more than one TEAE within different relationship categories within the same SOC/PT, only the worst case (greatest reported relationship) will be reported. A TEAE with an unknown relationship will be considered as treatment-related.

Frequency and percentage of subjects who experience TEAE will be summarized by SOC, PT, and severity (mild/moderate/severe). A severe adverse event is defined as any adverse events with a severity grade of 3 or higher. If a subject experiences more than one TEAE within different severity categories within the same SOC/PT, only the worst case (highest reported severity) will be reported. TEAE with an unknown severity will be considered as severe.

Frequency and percentage of subjects who experience TEAE will be summarized by SOC, PT, relationship, and severity (mild/moderate/severe). Each subject will be counted only once within a SOC or PT by using 1) the greatest reported relationship followed by 2) the highest reported intensity.

Frequency and percentage of subjects who experience a serious TEAE will be summarized by SOC and PT within SOC. Furthermore, frequency and percentage of subjects who experience a TEAE at the application site will be summarized by SOC and PT within SOC.

Listings of all AEs, all AEs leading to death, all serious AEs, all TEAEs leading to study or study drug discontinuation will be provided.

 INNOVADERM RESEARCH INC.	STATISTICAL ANALYSIS PLAN, Final V1.0Final 1.0
Protocol Number: AQR-151-212	Sponsor: Arcutis, Inc.

## 13.2 Clinical Laboratory

Descriptive statistics will be presented for data related to chemistry, hematology, and urinalysis. Change from baseline values will be presented for each post-baseline assessment. Frequencies and percentages for each result will be provided for qualitative urinalysis data.

Shift tables from baseline to the worst post-baseline assessment describing shifts to abnormality will be provided as well. Only subjects with a baseline result and a post-baseline result for the parameter will be considered.

Separate listings of all data for chemistry, hematology, urinalysis, and pregnancy tests will be provided.

Laboratory data will be presented in SI units.

## 13.3 Vital Signs

Descriptive statistics will be presented for data related to vital signs (systolic blood pressure diastolic blood pressure, heart rate, body temperature, and weight). Change from baseline values will be presented for each post-baseline assessment.

A shift table identifying subjects who gain or lose  $>5\%$  body weight over the course of the study will be provided. Only subjects with a baseline result and a result at the specified visit for the parameter will be considered.

A listing of all vital sign assessments will be provided.

## 13.4 Electrocardiogram (ECG)

Descriptive statistics will be presented for data related to ECGs (heart rate, RR duration, PR interval, QRS interval, QT interval, QTcB interval, and QTcF interval). Change from baseline values will be presented for each post-baseline assessment.

Shift tables from baseline to the worst post-baseline assessment describing shifts to abnormality for investigator overall interpretation will be provided as well.

A listing of the ECG assessments will be provided.

## 13.5 Local Tolerability Assessments

Investigator Local Tolerability Assessments

 INNOVADERM RESEARCH INC.	STATISTICAL ANALYSIS PLAN, Final V1.0Final 1.0
Protocol Number: AQR-151-212	Sponsor: Arcutis, Inc.

Local tolerability assessed by the investigator will be summarized by treatment and visit for dermal response on an 8-point scale (0-7). Furthermore, the frequency of subjects with each dermal response score as well as other effects (A to G) will be summarized by treatment and visit.

A sensitivity analysis of investigator local tolerability assessments will be conducted in which data from study sites 19, and 21 will be excluded. Due to a misunderstanding of the data collection form, data from both of these sites were initially assessed as disease assessments rather than local tolerability assessments. Data were updated after correct understanding of the CRF was attained, however, the effect of this post facto update of these data will be evaluated with this sensitivity analysis.

A listing of investigator local tolerability assessments will be provided.

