10.1.8 Local Tolerability Assessment

Investigator Local Tolerability Assessment will be performed as follows: Baseline, Week 1, Week 2, and Week 4.

Application site reactions will be graded at the timepoints outlined in the Schedule of Visits and Assessments ([Section 5](#)). Irritation reactions are graded using the scale detailed in the following section ([Berger 1982](#)). Reactions at the site of product application, which may occur post-Baseline, should be differentiated from the preexisting inflammation associated with the subject's AD.

The investigator assessments will be conducted by the investigator prior to study drug application in the clinic.

Dermal Response

- 0 = no evidence of irritation
- 1 = minimal erythema, barely perceptible
- 2 = definite erythema, readily visible; minimal edema or minimal papular response
- 3 = erythema and papules
- 4 = definite edema
- 5 = erythema, edema and papules
- 6 = vesicular eruption
- 7 = strong reaction spreading beyond application site

Other Effects

- A = slight glazed appearance
- B = marked glazing
- C = glazing with peeling and cracking
- D = glazing with fissures
- E = film of dried serous exudates
- F = small petechial erosions and/or scabs
- G = no other effects

The Subject Local Tolerability Assessment will be performed as follows: Baseline, Week 1, Week 2.

This assessment will be administered by the site 10 to 15 minutes after study drug application in the clinic at Baseline and at Weeks 1 and 2.

Grade	Sensation Following Drug Application
0 (none)	No sensation
1 (mild)	Slight warm, tingling sensation; not really bothersome
2 (moderate)	Definite warm, tingling sensation that is somewhat bothersome
3 (severe)	Hot, tingling/stinging sensation that has caused definite discomfort

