11.3.2 Local Tolerance Assessment

For the Investigator's assessment the numeric application site reaction scores will be summarized individually by using number and percentage of subjects by visit.

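### SAP 13.5 makes no within-subject use of the irritation score taken before the first application, and pre-specifies no check for eczema scored as irritation at sites other than 19 and 21

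*SAP*

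**What the plan says.** **The planned summary.** SAP 13.5 states: "Local tolerability assessed by the investigator will be summarized by treatment and visit for dermal response on an 8-point scale (0-7"). It adds counts of each score and of the lettered other effects, again by treatment and visit, and a listing. Protocol 11.3.2 has the same structure: "numeric application site reaction scores will be summarized individually by using number and percentage of subjects by visit". Neither document compares a subject's later score with that subject's Baseline score. For laboratory, vital sign and ECG data, SAP 13.2 to 13.4 plan both change from baseline and a shift table (for vital signs, the shift table covers body weight).

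**When the score is taken.** Protocol 10.1.8 states: "Investigator Local Tolerability Assessment will be performed as follows: Baseline, Week 1, Week 2, and Week 4". On timing it says: "The investigator assessments will be conducted by the investigator prior to study drug application in the clinic". The Baseline score therefore precedes any study drug in this trial. The same section tells investigators that: "Reactions at the site of product application, which may occur post-Baseline, should be differentiated from the preexisting inflammation" of the subject's eczema.

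**What went wrong at two sites.** SAP 13.5 reports that the form was misunderstood at sites 19 and 21, so that "data from both of these sites were initially assessed as disease assessments rather than local tolerability assessments". The data were updated once the form was understood. The SAP then plans: "A sensitivity analysis of investigator local tolerability assessments will be conducted in which data from study sites 19, and 21 will be excluded". The stated purpose is to gauge the effect of that later update. The SAP describes no check of the other sites, of which there are about 28 if about 30 opened as planned.

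**The concern.** A Dermal Response above 0 at Baseline cannot be a reaction to study drug applied in this trial. The scale grades erythema, edema and papules, which are also signs of eczema. Entry requires vIGA-AD 2 or 3 and EASI of at least 5 (Protocol 9.6.1), so a site that scored disease on this form should show non-zero Baseline scores in most or all of its subjects. The trial collects this check, and no planned analysis uses it.

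Eczema scored as irritation gives a score that falls as the eczema clears. The arm that clears more would then look better tolerated, whatever its true irritation.

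Local tolerability is a listed safety endpoint (SAP 2). Application-site reactions count as adverse events only if they need intervention, suspension or discontinuation (Protocol 10.7.1), so milder irritation is recorded mainly by the investigator's and the subject's scores. Only the investigator's score is taken at Week 4 (Protocol 10.1.8). If a pattern of raised Baseline scores were first noticed in unblinded tables, excluding further sites would be a post hoc decision.

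**Working it through.** The plan gives no figure to reproduce here. The check is a reading of the sections side by side and an illustration in which every rate is assumed.

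**Inputs from the documents:** 90 to 105 subjects at about 30 sites (Protocol 9.1); a score from 0 to 7 taken before application at Baseline and Weeks 1, 2 and 4 (Protocol 10.1.8).

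**Assumed inputs:** a share *f* of subjects, at sites other than 19 and 21, has eczema scored as irritation. Their score is 2 if eczema is visible and 0 if not. True irritation is 0 in everyone. All mis-scored subjects have visible eczema at Baseline. At Week 4 it persists in a share *pV* on vehicle and *pA* on active. The share *f* is the same in each arm.

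**1. Would the error leave a trace?** The expected number of non-zero Baseline scores among 90 subjects is 90 × *f*, shown in the table. These would appear in the Baseline column of the by-visit table.

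**2. Effect on the by-visit mean at Week 4.** Active minus vehicle = 2*f* × (*pA* − *pV*). With *pV* = 70%:

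| *f* | Non-zero at Baseline, of 90 | *pA* = 70% | *pA* = 50% | *pA* = 30% |
|---|---|---|---|---|
| 5% | 4.5 | 0 | −0.02 | −0.04 |
| 10% | 9 | 0 | −0.04 | −0.08 |
| 20% | 18 | 0 | −0.08 | −0.16 |
| 30% | 27 | 0 | −0.12 | −0.24 |

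**3. Effect on the by-visit percentages.** The spurious share with a non-zero Week 4 score is *f* × *pV* on vehicle and *f* × *pA* on active. At *f* = 10% and *pA* = 50%: 0.10 × 0.70 = 7% against 0.10 × 0.50 = 5%. At *f* = 30% and *pA* = 30%: 0.30 × 0.70 = 21% against 0.30 × 0.30 = 9%. If clearance is equal, the difference is zero at any *f*.

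**4. Would mean change from Baseline remove it?** No. (2*f·pA* − 2*f*) − (2*f·pV* − 2*f*) = 2*f* × (*pA* − *pV*), the same as in step 2.

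**5. Would a count of subjects above their own Baseline remove it?** In this model, yes. A mis-scored subject starts at 2 and is later at 2 or 0, so the worst later score never exceeds the Baseline score. The spurious count is 0 in both arms. The model leaves out eczema that worsens, which would still be counted at a misreading site.

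**The case against.** A reader might infer that mis-scoring at other sites would go undetected. The documents do not support that. The score frequencies by visit should include Baseline, a listing is planned and ordered by subject and visit (SAP 13.5 and Appendix 1), and the first two digits of the subject ID give the site (Protocol 9.4). The information is there; what is missing is a pre-specified use of it.

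A reader might also infer that the tolerability comparison is biased in favour of active. That would need two things the documents do not establish: that another site misread the form, and that active clears more eczema than vehicle. The second is the premise behind the sample size (a 35% difference in EASI change, SAP 5.1), but it is also what the trial is testing. Protocol 12.2 and 12.4 provide for monitoring and a full quality control check, which may have found any other such site.

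The exclusion of sites 19 and 21 does what it sets out to do. It tests a correction at the two corrected sites and was not meant as a search for others.

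Other tolerability evidence exists: the subject's own grade 10 to 15 minutes after application, at Baseline and Weeks 1 and 2, and a summary of application-site adverse events (SAP 13.1). All of it is descriptive, so no decision rule is at risk. Subject tolerability and PHQ-8 are also summarised by visit without change from baseline, so this format is not unusual within the SAP.

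These points limit the claim but do not remove it. The same form was misread at two sites, the plan specifies no look at the others, and a simple within-subject comparison is left out.

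**Conclusion.** The point holds as a gap in pre-specification. It does not show an error in the data. SAP 13.5 has no within-subject comparison with the pre-application score and no planned check for disease scoring beyond sites 19 and 21.

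The size is unknown. Under the assumed rates above, the spurious difference between arms at Week 4 runs from nothing, when clearance is equal, to 12 percentage points (21% against 9%) in the most extreme case shown. Any bias towards active depends on a further site having erred, on active clearing more eczema than vehicle, and on similar mis-scoring across arms.

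The change is worth making because it uses data already collected and costs little. It does not affect the efficacy analyses.

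**What to change.** In SAP 13.5:

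1. Add, by arm, a shift table from Baseline to the worst post-baseline Dermal Response, and the number of subjects whose worst post-baseline score exceeds their own pre-application score. Under SAP 5.6 a shift table would also take in scores from unscheduled visits, which the by-visit table omits.
2. Before database lock and while blinded, list non-zero Baseline Dermal Response scores by site. State in advance the rule for judging that a site scored disease, for example non-zero Baseline scores in most of its subjects. Add any such site to the sensitivity exclusion. Dropping a site for a single raised score would be too blunt: grade 1 is barely perceptible erythema, and at 90 to 105 subjects over about 30 sites each site has only 3 to 3.5 subjects on average.
3. Keep the by-visit table and the planned exclusion of sites 19 and 21.

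The cost is one added table and one blinded listing, with no new data. The downside is that the shift can understate true irritation where the Baseline score was already raised, and would still count worsening eczema at a site that misread the form. It therefore supplements the by-visit table and should not replace it.

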#### Subject Local Tolerability Assessments

Local tolerability assessed by the subject will be summarized by treatment and visit for tolerability grading on a 4-point scale (0-3). Furthermore, the frequency of subjects with each tolerability score will be summarized by treatment and visit.

A listing of subject local tolerability assessments will be provided.

### **13.6 Patient Health Questionnaire Depression Scale (PHQ-8)**

The Patient Health Questionnaire Depression Scale is an 8 question Assessment (see [Appendix 5](#)).

The PHQ-8 score is the sum of the responses for the 8 questions, each question ranging from 0 (Not at all) to 3 – (Nearly every day). Five severity categories of depression are defined as follows:

- None – Minimal depression (1 to 4)
- Mild depression (5 to 9)
- Moderate depression (10 to 14)
- Moderately severe depression (15 to 19)
- Severe depression (20 to 24)

The score will be set to missing in case of at least one missing value. The PHQ-8 score will be summarized by treatment and visit. Furthermore, the frequency of subjects within each severity category will be summarized by treatment and visit.

 INNOVADERM RESEARCH INC.	STATISTICAL ANALYSIS PLAN, Final V1.0Final 1.0
Protocol Number: AQR-151-212	Sponsor: Arcutis, Inc.

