### 3.5 Changes to the Analysis from the Protocol

The primary method of handling of missing data will be the MMRM method without explicit imputations for missing data as opposed to a multiple imputation technique.

The PHQ-8 scoring in the protocol describes "Severe Depression" as any score between 20 and 27. The PHQ-8 score has a maximum result of 24, The category has been corrected in [section 13.6](#) to a score between 20-24.

 INNOVADERM RESEARCH INC.	STATISTICAL ANALYSIS PLAN, Final V1.0Final 1.0
Protocol Number: AQR-151-212	Sponsor: Arcutis, Inc.

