### Scoring

If two consecutive numbers are circled, score the higher (more distress) number. If the numbers are not consecutive, do not score the item. Score is the sum of the 8 items. If more than 1 item missing, set the value of the scale to missing. A score of 10 or greater is considered major depression, 20 or more is severe major depression.

 INNOVADERM RESEARCH INC.	STATISTICAL ANALYSIS PLAN, Final V1.0Final 1.0
Protocol Number: AQR-151-212	Sponsor: Arcutis, Inc.

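### SAP 13.6 gives a PHQ-8 total of 0 no severity category and applies a stricter missing-item rule than its own Appendix 5, without declaring it

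*SAP*

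**What the plan says.** SAP 13.6 defines the score: "The PHQ-8 score is the sum of the responses for the 8 questions, each question ranging from 0 (Not at all) to 3". It then sets five severity bands. The lowest is "None – Minimal depression (1 to 4" and the highest "Severe depression (20 to 24". Two outputs are planned: a summary of the score, and a table in which "the frequency of subjects within each severity category will be summarized by treatment and visit".

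The bands come from protocol 10.1.6, which has the same lowest band and ends the highest at 27. SAP 3.5 corrects the upper limit because "The PHQ-8 score has a maximum result of 24". It says nothing about the lower limit.

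On incomplete forms, SAP 13.6 says: "The score will be set to missing in case of at least one missing value". SAP Appendix 5, which 13.6 cites for the instrument, says: "If more than 1 item missing, set the value of the scale to missing". Protocol Appendix 3 has the Appendix 5 rule. Appendix 5 also covers an item with two answers circled: "If the numbers are not consecutive, do not score the item". So an item can be unscored even on a form where every line was answered. SAP 3.5 does not mention the missing-item rule.

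**The concern.** PHQ-8 is a listed safety endpoint in SAP section 2, and protocol 7.3.2 gives the reason for watching mood: psychiatric events were more frequent on oral roflumilast (5.9%) than on placebo (3.3%). The category table is the output most readers will use to judge mood by arm, and it has two specification faults.

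First, a subject with no symptoms has no row. SAP Appendix 1 makes all subjects in the arm the default percentage denominator. Subjects scoring 0 and subjects with a blank score would then both appear only as a shortfall from 100%, and the table could not tell the best outcome from missing data.

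Second, the programmer has two incompatible rules for a form with one unscored item. If 13.6 is followed, that form leaves both summaries, however high its seven answered items total. SAP 13.1 to 13.5 and 13.7 each promise a listing; 13.6 specifies none, so no planned PHQ-8 output would show the omitted form.

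**Working it through.** **Inputs.** Eight items scored 0 to 3; bands 1–4, 5–9, 10–14, 15–19 and 20–24 (SAP 13.6); the two missing-item rules (SAP 13.6 and Appendix 5); 30 to 35 subjects per arm (SAP 5.1).

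**Reproducing the SAP's own figure.** Maximum = 8 × 3 = 24, as SAP 3.5 states. The protocol's 27 would need nine items (9 × 3).

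**Coverage of the bands.** Of the 25 possible totals (0 to 24), 24 fall in exactly one band. The only total without a band is 0. With the first band set to 0–4, all 25 are covered once.

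**Size of the gap (assumption).** The documents give no share of subjects scoring 0. If that share is f, the bands add up to 1 − f when no form is missing.

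- f = 10%: 0.10 × 30 to 0.10 × 35 = 3.0 to 3.5 subjects per arm without a category; bands sum to 90%.
- f = 30%: 9.0 to 10.5 subjects; bands sum to 70%.
- f = 50%: 15.0 to 17.5 subjects; bands sum to 50%.
- f = 70%: 21.0 to 24.5 subjects; bands sum to 30%.

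**One missing item.** Seven answered items sum to between 0 and 7 × 3 = 21. The missing item can add only 0 to 3. A seven-item sum of 15 therefore means a full total of 15 to 18, and a sum of 21 means 21 to 24. Any form at 15 or above on seven items is at 15 or above whatever the missing answer was. Under 13.6 it is blank; under Appendix 5 it keeps a score.

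**Share of forms blanked (assumption).** The documents give no item-missing rate. Let q be the rate per item, independent across items.

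- SAP 13.6: 1 − (1 − q)^8
- Appendix 5: 1 − (1 − q)^8 − 8q(1 − q)^7

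| q | SAP 13.6 | Appendix 5 |
|---|---|---|
| 0.5% | 3.9% | 0.07% |
| 1% | 7.7% | 0.27% |
| 2% | 14.9% | 1.0% |
| 5% | 33.7% | 5.7% |

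For q = 1%: 1 − 0.99^8 = 0.0773, and 0.0773 − 8 × 0.01 × 0.99^7 = 0.0773 − 0.0746 = 0.0027.

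**What Appendix 5 leaves open.** It defines the score as a sum of eight items but keeps a form with seven, without saying how. The choice matters near the cut-offs: a seven-item sum of 14 lies in the 10–14 band as it stands, but prorated it is 14 × 8/7 = 16, in the 15–19 band. With rounding to the nearest integer, six of the 22 possible seven-item sums change band when prorated: 4, 9, 13, 14, 18 and 19.

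**The case against.** The lowest band's label begins with None, and a total of 0 is the only score that plainly means none. A sensible programmer would probably count zeros there, and the numeric summary includes them in any case. That is fair, but a final SAP should not depend on the guess, particularly after the top of the same scale was checked and corrected.

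Percentages below 100% are not in themselves proof of a fault. With the Appendix 1 denominator, any missed visit produces a shortfall. This stands. The defect is that a total of 0 has no row, whatever the percentages add up to.

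Requiring all eight items is a defensible conservative choice, and SAP 12.1 does the same for EASI. This stands too. The fault is that the SAP contradicts its own appendix and does not declare the departure from the protocol; the stricter rule is not wrong in itself. Importing the Appendix 5 rule unchanged would bring in its gap on seven-item forms.

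A reader might infer that the table is wrong at both ends of the scale. The documents do not support that. The 20–24 band is correct, and the missing-item rule acts at every score level and puts no complete form in a wrong band.

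A reader might also infer that a subject at 15 or above could be missed clinically. Protocol 9.7, 10.1.6 and 10.9 handle that score subject by subject during the study, and nothing there depends on this end-of-study table. The C-SSRS listings and adverse event tables also cover psychiatric safety.

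**Conclusion.** Both faults are on the face of the SAP. A total of 0 has no severity category, which makes the category table incomplete as written. The missing-item rule in 13.6 conflicts with SAP Appendix 5 and protocol Appendix 3, and SAP 3.5 does not declare the change.

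The facts rest on no assumption; the size does. Between about 3 and 25 subjects per arm would lack a category at a visit if 10% to 70% scored 0, and the share of forms blanked by 13.6 would run from 3.9% to 33.7% for item-missing rates of 0.5% to 5%. None of these rates comes from the documents, and independence between items is also assumed.

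The consequence is limited to two descriptive safety summaries, for which SAP section 13 plans no formal inference. The primary analysis, power, alpha and on-study referral are unaffected. It should still be corrected, because the table reports a pre-specified safety endpoint and the correction is nearly free.

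**What to change.** 1. In SAP 13.6, set the lowest band to 0 to 4.
2. Reconcile 13.6 and Appendix 5 to one missing-item rule. If a form with one missing item is kept, state whether its score is the seven-item sum or the prorated value (sum × 8/7) and, if prorated, how it is rounded. If complete forms are required, annotate Appendix 5 to say that 13.6 overrides its scoring note.
3. Record both changes in SAP 3.5: the band, because the gap comes from protocol 10.1.6, and the missing-item decision, because protocol Appendix 3 has its own rule.

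The cost is a few lines of SAP text and the matching programming specification. No new data, analysis or sample size is needed.
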